NON-INTERVENTIONAL (NI) STUDY PROTOCOL

Study Information

Title	Patient Characteristics, Treatment Patterns, and Clinical Outcomes in Patients Diagnosed with HR+/HER2- Advanced/Metastatic Breast Cancer Receiving CDK4/6i + Aromatase Inhibitor (AI) Combination Therapy as Initial Endocrine-based Treatment
Protocol number	A5481144
Protocol version identifier	1.0
Date	05 November 2019
Active substance	Palbociclib (L01XE33)
Medicinal product	Palbociclib
Research question and objectives	
Primary Objectives:
 
Objective 1 - Among patients with HR+/HER2- advanced/metastatic breast cancer (A/MBC) receiving CDK4/6i +AI combination therapy as initial endocrine-based therapy:
 
Describe demographic and clinical characteristics.Describe treatment patterns (eg, regimen sequencing, dose changes, discontinuations). 
Objective 2 - Among patients receiving Palbociclib + AI as initial endocrine-based therapy, examine clinical effectiveness outcomes including real-world progression-free survival (rwPFS), overall survival (OS), and real-world tumor response (rwTR).

PFIZER CONFIDENTIAL

[REDACTED]

	CCI [REDACTED]
	[REDACTED]
Author	PPD PhD, MStat PPD [REDACTED] Phone: PPD Email: PPD PPD MPH PPD [REDACTED] Phone: PPD Email: PPD PPD MA PPD [REDACTED] Phone: PPD Email: PPD

2. LIST OF ABBREVIATIONS

[figure not shown]
Abbreviation	Definition
A/MBC	Advanced/metastatic breast cancer
AE	Adverse event
AEM	Adverse event monitoring
AI	Aromatase inhibitor
CDK4/6i	Cyclin-dependent kinase 4/6 inhibitor
CFR	Code of Federal Regulations
CR	Complete response
CRN	Clinical Research Nurse
DCT	Data collection tools
ECOG	Eastern Cooperative Oncology Group
EMR	Electronic medical record
ER	Estrogen receptor
ESMO	European Society for Medical Oncology
FDA	Food and Drug Administration
HEOR	Health Economics and Outcomes Research
HER2	Human epidermal growth factor receptor 2
HR	Hormone receptor; hazard ratio
IRB	Institutional review board
IRIS	Ibrance Real World Insights Study
NE	Not evaluable
NIS	Non-interventional study
OS	Overall survival
PFS	Progression-free survival
PD	Progressive disease
PR	Progesterone receptor; partial response
rwPFS	Real-world progression-free survival
rwTR	Real-world tumor response
SAP	Statistical analysis plan
SD	Stable disease
SQL	Structured query language
SSDI	Social Security Death Index
UD	Undocumented
U.S.	United States

4. ABSTRACT

Title: Patient Characteristics, Treatment Patterns, and Clinical Outcomes in Patients Diagnosed with HR+/HER2- Advanced/Metastatic Breast Cancer Receiving CDK4/6i + AI Combination Therapy as Initial Endocrine-based Treatment.

Rationale and Background: The treatment landscape for HR+/HER2- advanced and metastatic breast cancer (A/MBC) has changed as multiple CDK4/6i drugs in combination with aromatase inhibitor (AI) are approved for use in the first line and subsequent lines. The present study is designed to describe treatment patterns and clinical outcomes in patients diagnosed with HR+/HER2- A/MBC who received CDK 4/6i combination therapy with AI as initial endocrine-based treatment in the U.S. community oncology setting.

Research Question and Objectives: The objective of this study is to describe the patient characteristics, treatment patterns, and clinical effectiveness outcomes for patients with a diagnosis of HR+/HER2- A/MBC who received CDK4/6i combination therapy with AI as the initial endocrine-based therapy in the A/MBC setting.

Primary Objectives:

Objective 1 – Among patients with HR+/HER2- advanced/metastatic breast cancer (A/MBC) receiving CDK4/6i combination therapy with AI as initial endocrine-based therapy:

- a. Describe demographic and clinical characteristics.
- b. Describe treatment patterns (eg, regimen sequencing, dose changes, discontinuations).

Objective 2 – Among patients receiving Palbociclib + AI as initial endocrine-based therapy, examine clinical effectiveness outcomes including real-world progression-free survival (rwPFS), overall survival (OS), and real-world tumor response (rwTR).

CCI

Study Design: This is a retrospective, observational study that will document the treatment patterns and clinical outcomes of patients diagnosed with HR+/HER2- A/MBC who received CDK4/6i combination therapy with AI as the initial endocrine-based therapy in the A/MBC setting.

Population: The study will include adult patients 18 years or older, diagnosed with HR+/HER2- A/MBC who initiated CDK4/6i combination therapy with AI as the initial endocrine-based therapy on or after 2/3/2015 and before 4/1/2019. Patients for this study will be identified through Structured Query Language (SQL) queries of the United States oncology electronic medical record (EMR) data available to Concerto HealthAI, including data from CancerLinQ-affiliated practices, referred to as the Definitive Oncology Dataset.

Variables: Patient demographics, clinical characteristics, treatment patterns, and clinical effectiveness outcomes will be collected and analyzed.

Data Source: Concerto HealthAI maintains a network of community oncology practices representing a geographically and demographically diverse patient population. Data from these practices have been collected centrally in the Definitive Oncology Dataset, which is the source of data to be collected in this study.

Study Size: All patients meeting the eligibility criteria from Definitive Oncology Dataset will be included in the study (estimated 1100 –1300 patients).

Data Analysis: Descriptive analysis will be conducted to describe patient demographics, clinical characteristics, treatment patterns (eg, regimen sequencing, dose changes, discontinuations), and clinical effectiveness outcomes (rwPFS, OS, rwTR).

CCI

[figure not shown]

- 
- 
- 
- 
- 
- 

[figure not shown]
5. AMENDMENTS AND UPDATES

None.

PFIZER CONFIDENTIAL

CCI

7. RATIONALE AND BACKGROUND

It is estimated that 42,260 people (41,760 female and 500 male) in the United States (U.S.) will die of breast cancer in 2019. Breast cancer is the second leading cause of cancer death for women after lung cancer.¹ Despite advances in the treatment of breast cancer, the prognosis for advanced and metastatic breast cancer (A/MBC) has been poor, with median survival generally under two years in first-line treatment Phase III trials depending on subtype,^{2,3} and slightly less in routine clinical practice.⁴ In patients with hormone receptor positive (HR+) and human epidermal growth factor receptor 2 negative (HER2-) disease, overall survival (OS) ranged from 38.5 – 60.1 months.⁵

About 71% of all breast cancers are HR+ and HER2-.⁶ HR+/HER2- A/MBC presents a challenge because patients with exposure to prior hormonal therapy, including aromatase inhibitor (AI) treatment, ultimately develop resistant disease.⁷ The treatment landscape for patients with HR+/HER2- A/MBC has changed with the approval of Palbociclib in February 2015 as the first in class cyclin-dependent kinase 4/6 inhibitor (CDK4/6i) indicated for the first treatment for HR+/HER2- A/MBC in combination with letrozole and subsequently expanded to all AIs as well as for the treatment of male breast cancer. Additional CDK4/6i therapies, ribociclib and abemaciclib, were approved in 2017 and 2018, respectively, for use in first line therapy as well. All of the CDK4/6i therapies also received FDA approval for use in combination with fulvestrant for patients who progressed after prior endocrine therapy.⁸

Real-world outcomes for patients with A/MBC who were treated with palbociclib in combination with AI or fulvestrant have been reported in several publications and at medical congresses. A comparative analysis of palbociclib + letrozole vs. letrozole alone was presented at the European Society for Medical Oncology (ESMO) 2019 congress.⁹ Using the Flatiron Health Analytics Database consisting of U.S. community physicians, a total of 1,416 electronic health records of patients with HR+/HER2- MBC were reviewed to assess the comparative effectiveness of palbociclib + letrozole (n=798) compared to letrozole alone (n=618). Results showed that patients who took palbociclib + letrozole had a median progression-free survival (PFS) of 24.5 months while patients on letrozole alone had a median PFS of 17.1 months (HR=0.68, 95% CI: 0.56-0.84). OS was also favorable for patients taking palbociclib + letrozole compared to patients taking letrozole alone (HR=0.57, 95% CI: 0.41-0.79). Another study reported on the Ibrance Real World Insights

Study (IRIS) involving medical chart review of 652 U.S. patients with A/MBC treated with palbociclib in combination with either AI (n=360) or fulvestrant (n=292).¹⁰ The 12-month progression-free rate was 84.1% for patients treated with palbociclib + AI and 79.8% for those treated with palbociclib + fulvestrant. The 12-month survival rates were 95.1% for palbociclib + AI and 87.9% for palbociclib + fulvestrant.

This present study is designed to examine further real-world evidence on the use of palbociclib, ribociclib, and abemaciclib in both male and female patients with A/MBC. This study is designed to describe patient characteristics, treatment patterns, and clinical effectiveness outcomes in a cohort of patients diagnosed with HR+/HER2- A/MBC who were treated with any CDK4/6i combination therapies with AI in the U.S. community oncology setting.

8. RESEARCH QUESTION AND OBJECTIVES

The objective of this study is to describe the patient characteristics, treatment patterns, and clinical effectiveness outcomes for patients with a diagnosis of HR+/HER2- A/MBC who received CDK4/6i combination therapy with AI as the initial endocrine-based therapy in the A/MBC setting.

Primary Objectives:

1. Among patients with HR+/HER2- A/MBC receiving CDK4/6i combination therapy with AI as initial endocrine-based therapy:
 - a. Describe demographic and clinical characteristics.
 - Demographic characteristics will include age, sex, race, insurance status, menopausal status, and region of residence at A/MBC diagnosis;
 - Clinical characteristics will include stage of initial diagnosis, histology, Eastern Cooperative Oncology Group (ECOG) performance status (where available, Karnofsky performance status will be converted to corresponding ECOG score) and comorbid disease burden, HER2 and Estrogen receptor (ER)/Progesterone receptor (PR) status, number and sites of distant metastasis at A/MBC diagnosis (if applicable); modalities of treatment received prior to A/MBC diagnosis (chemotherapy, hormone therapy, surgery, radiation therapy) and disease free interval (time between completion of adjuvant therapy and diagnosis of A/MBC).
 - b. Describe treatment patterns.
 - Distribution of regimens from the diagnosis of A/MBC through the end of the record;

- Sequence of regimens across lines, through the end of the record of systemic therapy;
- Description of the dosing employed with administration of palbociclib, ribociclib, and abemaciclib. Description of the dosing will include the starting dose, end dose, dose adjustment (dose increase and dose reduction), reasons for dose adjustment (dose modification, schedule changes, dose delay, hold, or discontinuation), discontinuation, reason, and time to dose adjustment (discontinuation).

2. Among patients receiving Palbociclib + AI as initial endocrine-based therapy, examine clinical effectiveness outcomes including:
 - a. Real-world progression-free survival (rwPFS) will be assessed for the first endocrine-based therapy.
 - b. Overall survival (OS) will be assessed from start of the first endocrine-based therapy.
 - c. Real-world tumor response (rwTR) will be assessed as best overall response for each regimen received within the first endocrine-based therapy.

CCI [REDACTED]

[REDACTED]

[REDACTED]

[REDACTED]

9. RESEARCH METHODS

9.1. Study Design

This is an observational, retrospective study involving medical chart review. Eligible patients will be identified and accrued from the Concerto HealthAI Definitive Oncology Dataset. All study data are secondary data and will have been collected retrospectively from existing clinical data originally collected as part of routine care.

9.2. Setting

9.2.1. Inclusion Criteria

Patients must meet all of the following inclusion criteria to be eligible for inclusion in the study:

1. Female or male sex.

PFIZER CONFIDENTIAL

[REDACTED]

2. Diagnosis (confirmed by clinical review) of A/MBC, defined as breast cancer at stage IIIB, stage IIIC, stage IV or identified as having distant metastasis.
3. Age ≥ 18 years at A/MBC diagnosis.
4. Initiated a CDK4/6i in combination with an AI as initial endocrine-based therapy after A/MBC diagnosis on or after 2/3/2015 and before 4/1/2019.
 - Note that the date of the start of the inclusion period reflects the month that the first CDK4/6i (ie, Palbociclib) received U.S. FDA approval.
5. Evidence of ER or PR positive disease, or absence of any indication of ER and PR negative disease closest to A/MBC diagnosis (ie, patients are eligible without affirmative indication of ER/PR+ status as long as ER/PR- indication is not present).
6. Evidence of HER2 negative disease, or absence of any indication of HER2 positive disease closest to A/MBC diagnosis (ie, patients are eligible without affirmative indication of HER2- status as long as HER2+ indication is not present).

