9.3.2. Curated Data

Data abstracted by Clinical Research Nurses (CRNs) will include the following:

1. Race/Ethnicity.
2. Date of initial diagnosis of breast cancer.
3. Stage at initial diagnosis of breast cancer.
4. Modalities of treatment received at any point prior to A/MBC diagnosis (Surgery, Radiation, Chemotherapy, Hormone therapy). This variable will be collected as “Yes” or “Not Documented” for each modality. The last date of systemic therapy, including hormonal therapy, administered in the adjuvant setting prior to stage IV/MBC diagnosis will be documented, if applicable.
5. Among patients who have a record of hormone therapy prior to A/MBC diagnosis, the name(s), and start and end dates of the hormonal agents received in the adjuvant setting will be collected.

6. Status of the patient as having progressed at any point after initiation of the first hormone therapy in the adjuvant setting, prior to A/MBC diagnosis (Y/N). If yes, the date of first disease progression/recurrence following initiation of hormone therapy in the adjuvant setting will be collected.
7. Date of A/MBC diagnosis. This date defines the index date for the study, as referenced below in describing other study variables.
8. Stage at index date (IIIB, IIIC, or IV).
9. For patients documented as Stage IIIB or IIIC at index date, the date of Stage IV/metastatic diagnosis will be collected, if applicable, from the index date through the end of the record or the end of the study, whichever occurs first.
10. Sites of distant metastasis at index date, if applicable (Bone; Chest Wall; Contralateral Breast; Distant Lymph node(s); Liver; Lung; Peritoneum; Pleural nodules; Malignant pleural effusion; Skin; Brain; Undocumented; Other, Specify).
11. Disease histology (Adenoid cystic; Cribriform; Ductal; Inflammatory; Intraductal; Lobular; Medullary with lymphoid stroma; Medullary, NOS; Mucinous; Paget's disease and infiltrating; Paget's disease and intraductal; Papillary; Secretory; Squamous cell; Tubular; Undifferentiated; Undocumented, Other, specify) nearest in time to index date.
12. ER status nearest in time to index date.
13. PR status nearest in time to index date.
14. HER2 status nearest in time to index date.
15. Menopausal status (Pre, Peri, Post, UD) nearest in time to the date of, but before, index date. Date of documentation will be collected.

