4.2. Subgroups

Summaries of study outcomes may be repeated focusing alternatively on but not limited to the following subgroups of interest—sample size permitting—which will be defined on the basis of:

- Age (years): ≤ 50 , 51-64, 65-74, ≥ 75 ;
- Gender, if number of males is low then we can restrict results to females;
- Race: White, Black, Other;
- Disease stage at initial diagnosis: I or II, III, IV;
- ECOG performance status: 0, 1 or 2, ≥ 3 ;
- Site of metastasis: Visceral, Non-visceral, Bone only;
- Number of metastatic sites: 1, 2, ≥ 3 ;

PFIZER CONFIDENTIAL

- Menopausal status: premenopausal, perimenopausal, Postmenopausal, undocumented;
- Hormone therapy prior to A/MBC diagnosis: yes, no;
- Chemotherapy prior to A/MBC diagnosis: yes, no;
- Surgery prior to A/MBC diagnosis: yes, no;
- Radiation therapy prior to A/MBC diagnosis: yes, no;
- Disease free interval: ≤ 12 months, > 12 months;
- Starting dose: by starting dose levels for Palbociclib, CCI

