5.1. DEMOGRAPHIC AND CLINICAL CHARACTERISTICS

Variable	Operational definition
Demographic characteristics	
Age	Age at A/MBC diagnosis, years
Age category	≤ 50 , 51-64, 65 –74, ≥ 75 years
Sex	Female or Male
Race	White, Black, Asian, Other, Unknown
Region of residence	Based on state where the patient resides: Northeast, Midwest, South, West
Insurance status	Private only, public only, public and private, or neither reported at index date and reported at initiation of the earliest endocrine-based therapy after the index date.
Clinical characteristics	
Menopausal status	(Pre, Peri, Post, UD) nearest in time to the date of, but before, index date.
Type of MBC	De novo MBC (newly diagnosed): Stage 4 at initial BC diagnosis Recurrent MBC: Stages 0-3 at initial BC diagnosis
Modalities of treatment received at any point prior to A/MBC diagnosis	Surgery (yes/no), Radiation (yes/no), Chemotherapy (yes/no), Hormone therapy (yes/no)

PFIZER CONFIDENTIAL

ECOG performance score	ECOG performance at index date (\pm 60 days), 0, 1,2,3,4,5, or missing. Where available, Karnofsky performance status will be converted to the corresponding ECOG score.
Disease stage at initial BC diagnosis	Stage I, II, III, IV, unknown/ undocumented
Disease stage at index date (date of A/MBC diagnosis)	IIIB, IIIC, or IV
Time from initial BC diagnosis to first MBC diagnosis	Months from the date of initial BC diagnosis to the date of metastatic diagnosis.
Disease free interval	The number of months between completion of adjuvant therapy and diagnosis of A/MBC.
Sites of distant metastasis at index date	Bone; Chest Wall; Contralateral Breast; Distant Lymph node(s); Liver; Lung; Peritoneum; Pleural nodules; Malignant pleural effusion; Skin; Brain; Undocumented; Other Specified. All sites will be reported as (yes/no).
Visceral metastasis at index date	Metastasis at one or more of the following sites: liver, pancreas, intestines, lung, heart, malignant pleural effusion, peritoneum, pleura. Other metastasis sites, including bone or non-visceral metastasis, may be present.
Non-visceral metastasis at index date	Metastasis at one or more of the following sites: bone, brain, skin, chest wall, contralateral breast, or distant lymph nodes.
Bone-only metastasis at index date	Bone metastasis, with no metastasis at any other identified site

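### When stage IIIB/IIIC disease is treated with adjuvant intent and later relapses, the index date stays at the stage III diagnosis, leaving eligibility unsettled and making the disease-free interval negative

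*Protocol*

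**What the plan says.** - **Definition of A/MBC.** Protocol 9.2.1 item 2 (repeated in SAP 4.1.1) counts "defined as breast cancer at stage IIIB, stage IIIC, stage IV or identified as having distant metastasis". Treatment intent plays no part.
- **Index date.** Protocol 9.3.2 item 7 reads "Date of A/MBC diagnosis. This date defines the index date for the study"; SAP 5 agrees. Item 8 allows the stage at index to be IIIB or IIIC. Item 9 adds: "For patients documented as Stage IIIB or IIIC at index date, the date of Stage IV/metastatic diagnosis will be collected, if applicable". A later metastatic diagnosis is thus a separate field and does not move the index.
- **Eligibility.** Under item 4 of Protocol 9.2.1, CDK4/6i + AI must be the first endocrine-based treatment following A/MBC diagnosis. No exception is made for adjuvant endocrine therapy. The abstract and Protocol 8 speak instead of initial therapy in the A/MBC setting.
- **Adjuvant end date.** Protocol 9.3.2 item 4 says the last systemic therapy "administered in the adjuvant setting prior to stage IV/MBC diagnosis will be documented".
- **Disease-free interval.** SAP 5.1 defines it as "The number of months between completion of adjuvant therapy and diagnosis of A/MBC", as does Protocol 8. SAP 4.2 uses it as a subgroup: "Disease free interval: ≤ 12 months, > 12 months".
- **Other fields tied to the earlier date.** Prior modalities and the names and dates of adjuvant hormonal agents cover the period before A/MBC diagnosis (9.3.2 items 4 and 5). Endocrine sensitivity is defined before index (9.3.4 item 5). Regimen distribution starts at A/MBC diagnosis (Protocol 8), and duration of follow-up starts at index (SAP 5.3).

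**The concern.** The rules suit two kinds of patient: one with stage I to IIIA disease who later becomes metastatic, and one with IIIB/IIIC disease who receives CDK4/6i + AI for that disease. They do not suit a third: IIIB/IIIC disease treated with surgery and adjuvant therapy, which relapses years later and is then treated with CDK4/6i + AI. That patient's index date is the stage III diagnosis, so the whole adjuvant course lies after index.

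Two things are at stake. Entry to the cohort may depend on initial stage for no stated reason. And for those who enter, several Objective 1 descriptors take values that do not mean what their names say, chiefly disease-free interval, prior treatment and endocrine sensitivity. Some outcome summaries may then place these patients in the wrong disease-free-interval subgroup. The stage IV cut-off in 9.3.2 item 4 suggests that adjuvant therapy after a IIIB/IIIC diagnosis was foreseen, but the index rule makes no provision for it.

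**Working it through.** **1. The plan's own figure.** Protocol 9.5 gives average follow-up as (50/2) + 8 = 33 months. With 30.4375 days per month, 3 February 2015 to 1 April 2019 is 49.9 months and 1 April to 1 December 2019 is 8.0 months, so 49.9/2 + 8.0 = 32.95. The figure reproduces. It does not enter the interval below. It matters only because 9.5 calls those dates a window for diagnosis, whereas 9.2.1 item 4 applies them to treatment start.

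**2. Order of dates.** For adjuvant-treated IIIB/IIIC disease that relapses, the order is: IIIB/IIIC diagnosis (index), end of adjuvant therapy, stage IV relapse.

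- As written: interval = index date − adjuvant end date, which is below zero for every such patient.
- To relapse: interval = stage IV date − adjuvant end date, which is positive in this order.

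**3. Illustration.** All patient dates are assumed. Stage IV relapse is June 2018 in each case, with CDK4/6i + AI started after it and before 1 April 2019. Follow-up runs to December 2019.

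| Case | IIIB diagnosis | Adjuvant therapy and end | Interval as written | Interval to stage IV | Follow-up from index | Follow-up from stage IV |
|---|---|---|---|---|---|---|
| a | June 2015 | chemotherapy only, January 2016 | -7.0 | +29.0 | 54.0 | 18.0 |
| b | June 2015 | including endocrine, January 2018 | -31.0 | +5.0 | 54.0 | 18.0 |
| c | June 2010 | endocrine, December 2015 | -66.0 | +30.0 | 114.0 | 18.0 |

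(Intervals and follow-up in months.)

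A negative value falls in the subgroup of 12 months or less. Cases a and c belong in the other subgroup when measured to relapse. Case b stays in the same subgroup either way, but its value is still wrong.

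**4. Criterion 4.** In b and c the first endocrine-based therapy after the IIIB diagnosis is the adjuvant agent. Read literally, both fail. A stage II or IIIA patient with the same treatment dates and relapse passes, because that patient's A/MBC diagnosis is the relapse. If adjuvant therapy is disregarded as lying outside the A/MBC setting, b and c enter with the negative intervals shown. Case a enters on either reading.

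**5. Other fields for a retained patient.**

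- The modality fields stop at A/MBC diagnosis and miss the adjuvant treatment.
- Where adjuvant endocrine therapy was given, sensitivity cannot be derived as defined, because that therapy comes after index.
- Adjuvant systemic agents enter the regimen distribution as A/MBC treatment.
- Follow-up is counted from the stage III date: 54 or 114 months in the table, against 18 from metastatic diagnosis.

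**6. A further sign of two anchors.** SAP 5.1 measures time from initial diagnosis to the metastatic diagnosis. The matching row in Table 2a is labelled as running to the first A/MBC diagnosis. For a IIIB/IIIC index these are different dates.

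**The case against.** The strongest reply is that exclusion is only one reading. The protocol generally places the adjuvant setting before A/MBC, its objectives refer to the A/MBC setting, and SAP 5.1 classes stages 0-3 at initial diagnosis as recurrent MBC. Relapsed stage III patients are therefore expected in the cohort, and nurse abstractors confirm eligibility by chart review. This stands in part: a reader might infer that these patients are definitely excluded, and the documents do not establish that. But stage IIIA alone could fill the recurrent stage III group, the first-A/MBC label in Table 2a points the other way, and abstractors have no rule to apply consistently. The lenient reading also leads straight to the negative interval.

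Other stronger inferences are not supported:

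- **A head count.** One might apply an assumed 5-10% to the 1100-1300 patients and get 55 to 130. The documents give no share, and 1100-1300 estimates patients who already meet the criteria, so it cannot be the base for those excluded.
- **Lost treatment history.** Only the fields before A/MBC are affected. Systemic agents after index are still captured (9.3.2 items 21 and 22; 9.3.3 item 5), though as A/MBC treatment. The adjuvant end date and stage IV date are also collected, so a correct interval can be computed.
- **Biased survival origins.** rwPFS and OS run from the start of initial endocrine-based therapy (SAP 5.3), so their time origins do not move.
- **Every relapsed stage III patient.** If the diagnosis window in Protocol 9.5 governs, case c drops out and fewer patients are affected; a and b remain. Without adjuvant systemic therapy the interval is missing, not negative.

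It is also fair that the disease-free-interval subgroups are optional and that no hypothesis is tested.

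**Conclusion.** The point holds as a defect in stated definitions. Adjuvant dates run to stage IV, disease-free interval runs to A/MBC diagnosis, and the index stays at the IIIB/IIIC date. Together these give a negative interval for every retained patient whose IIIB/IIIC disease received adjuvant systemic therapy and later relapsed. Whether those given adjuvant endocrine therapy are retained at all is unsettled.

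The effect is on cohort composition, Objective 1a descriptors, regimen distribution, duration of follow-up and any summaries by disease-free interval. The error per patient can be large (-7 against +29 months in case a, on assumed dates). The number of patients cannot be computed from the documents. The conclusion rests on the index rule as written, under which a later stage IV diagnosis does not reset the date. It should be corrected before curation, because it yields wrong values and does not merely leave a detail open.

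**What to change.** In Protocol 9.2.1, Protocol 9.3.2 item 7 and SAP 5, state that for stage IIIB/IIIC disease treated with adjuvant intent that later recurred:

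1. the index date is the date of recurrence or stage IV diagnosis (the stage IV date is already collected under item 9);
2. adjuvant endocrine therapy does not count as the initial endocrine-based therapy under criterion 4;
3. the same date anchors disease-free interval, prior modalities, adjuvant dates and endocrine sensitivity.

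The IIIB/IIIC date remains the index where the qualifying therapy was given for that disease. At the least, measure disease-free interval to the recurrence or stage IV date in Protocol 8 and SAP 5.1, in line with 9.3.2 item 4.

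The cost is a wording amendment and an adjusted screening query, some extra charts to screen, and a recurrence date to abstract for the few relapses that are not metastatic. It is cheapest before curation begins. This changes data definitions only; no clinical rule is involved.
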